7.6.1. Preparing the Study Medication for Application

To perform a study medication treatment for Target and Non-Target Warts a staff member will select the appropriate study medication applicator. The following instructions outline the procedure for application of the study medication to the Target and Non-Target Warts:

- Investigational Study Staff member will prepare the A-101 study medication applicator for all subjects, regardless of age by:
 - Washing their hands prior to, and after completing the study medication treatments
 - Wear safety glasses and nitrile or vinyl examination gloves during the treatment; latex gloves are prohibited
 - Complete the study medication applicator label as instructed
 - Visually inspect the applicator for damage:
 - If the applicator appears damaged do not use it for the treatment, contact the study monitor for disposal instructions and select another unused applicator for treatment.

Page 26 of 53 Amendment 2 Version 3 Date: 05 December 2017

If the applicator is intact, proceed with the applicator preparation process as outlined in Figure 1.

Step 1: Hold the Study Medication applicator so that the applicator cap is pointing up.

Step 2: Crush the ampule in the applicator by applying pressure at the center of the barrel of the applicator.

sleeve.

Step 3: Remove the cardboard Step 4: Tap the barrel of the applicator to ensure the solution is free of the crushed ampule.

Page 27 of 53 Amendment 2 Version 3 Date: 05 December 2017

Figure 1: Diagram Showing the Process for Preparing A-101 Study Medication

7.6.2. Applying Study Medication to Target and Non-Target Warts on the Trunk and Extremities

Subjects that are between the ages of 8 and 17 will have their A-101 study medication applied by the investigational study staff and the staff will follow the application process outlined below for all Target and Non-Target Warts.

Subjects 18 years of age and older will apply their A-101 study medication to his/her identified Target and Non-Target Warts in the presence of the treating physician or member of the investigational staff.

The following instructions will be used by all individuals applying A-101 study medication to all Target and Non-Target Warts:

- Do not apply the study medications to eyes, nose, mouth, mucous membranes, or open wounds
- Thoroughly cleanse the Target and Non-Target Warts by firmly rubbing with a swab/wipe wetted with 70% isopropyl alcohol
- Using firm pressure and with the tip of the applicator held over the wart, squeeze in the middle of the applicator to apply one drop of study medication onto the Target Wart. Using the smaller side of the applicator tip, move the applicator around in a circular motion to fully saturate the lesion. Apply the study medication for approximately 15 seconds.
- Minimize exposure to the surrounding normal skin
- During the treatment process remove excess study medication from the surrounding skin using a clean absorbent wipe
- Ensure that each identified wart is fully saturated with study medication at the end of the \sim 15 second application
- Allow the treated wart to remain undisturbed for ~ 15 seconds

Page 28 of 53 Amendment 2 Version 3 Date: 05 December 2017

- After ~15 seconds repeat the ~15 second application process
- Repeat the application/waiting cycle until the study medication has been applied to each identified Wart up to 3 times.

Document the number of times each identified wart is treated during a treatment Visit.

After all identified warts have been treated, the subject must be instructed not to disturb any of the treated warts until just prior to the post-application LSR evaluation.

Just prior to the post-application LSR evaluation the investigational study staff should absorb any remaining A-101 study medication and dry the Target and Non-Target Warts and the surrounding skin without wiping or rubbing

It is acceptable to treat multiple Target/Non-Target Warts at the same time if, in the investigator's opinion, it is practical without exposing non-lesional skin to the study medication.

7.7. Dose modification

If a subject refuses to allow a study medication initial treatment or retreatment the investigator must report the visit number, visit date, Target Wart number(s) the subject refused to allow treatment for and the reason for the refusal in the subject's CRF.

If the subject's refusal is associated with an AE, the investigator must also report the event on the appropriate CRF.

Page 29 of 53 Amendment 2 Version 3 Date: 05 December 2017

7.8. Previous and Concomitant Therapies

7.8.1. **Previous therapies**

During Visit 1, the investigator or designee will question the subject to ensure they have not used any excluded therapies within the specified period prior to Visit 1 to any of the Target or Non-Target Warts:

- Intralesional Therapy
 - Immunotherapy (e.g., *Candida* antigen, mumps antigen, *Trichophyton* antigen) 8 weeks
 - o Anti-metabolite therapy (e.g., bleomycin, 5-fluorouracil); 8 weeks
- Systemic Therapy
 - Immunomodulatory/immunosuppressant therapy (e.g., etanercept, alefacept, infliximab); 16 weeks
 - o Glucocortico-steroids (inhaled and intra-nasal steroids are permitted); 28 days
- Topical Therapy
 - LASER (e.g., pulsed-dye laser [PDL], light (e.g., intense pulsed light [IPL], photodynamic therapy [PDT], other energy based therapy); 180 days
 - Immuno-therapy (e.g., imiquimod, squaric acid dibutyl ester [SADBE], etc.); 12 weeks
 - Anti-metabolite therapy (e.g., 5-fluorouracil); 8 weeks
 - Retinoids; 90 days
 - Liquid nitrogen, electrodesiccation, curettage; 60 days
 - Over-the-counter (OTC) wart therapies; 28 days

7.8.2. Concomitant therapies

Concomitant therapies are any new or existing therapy received from Visit 1 until discharge from the study.

Concomitant therapies include drug (*e.g.*, prescription, over-the-counter [OTC]) and non-drug (*e.g.*, chiropractic, physical therapy, energy-based treatments) therapies. Subjects will refrain from using any prohibited therapies in compliance with the inclusion/exclusion criteria. Subjects should refrain from changing the use of any concomitant therapies during the study.

All new or modified concomitant therapies used during the study must be recorded in the subject CRF.

7.8.3. Prohibited therapies

During the course of this study, subjects are prohibited from using the following treatment therapies to treat any of the Target or Non-Target Warts:

Page 30 of 53 Amendment 2 Version 3 Date: 05 December 2017

- Intralesional Therapy
 - Immunotherapy (e.g., *Candida* antigen, mumps antigen, *Trichophyton* antigen)
 - Anti-metabolite therapy (e.g., bleomycin, 5-fluorouracil);
- Systemic Therapy
 - Immunomodulatory/immunosuppressant therapy (e.g., etanercept, alefacept, infliximab);
 - Glucocortico-steriods (inhaled and intra-nasal steroids are permitted);
- Topical Therapy
 - LASER (e.g., pulsed-dye laser [PDL], light (e.g., intense pulsed light [IPL], photodynamic therapy [PDT], other energy based therapy);
 - Immuno-therapy (e.g., imiquimod, squaric acid dibutyl ester [SADBE], etc.);
 - Anti-metabolite therapy (e.g., 5-fluorouracil);
 - Retinoids;
 - Liquid nitrogen, electrodesiccation, curettage;
 - Over-the-counter (OTC) wart therapies;

The investigator should notify the Medical Monitor immediately if any prohibited therapies are required to ensure subject safety.

Starting with Visit 2, subjects must not apply any topical products (*e.g.*, moisturizers, sunscreens, etc.) to their Target or Non-Target Warts within **12 hours prior** to any study visit (Note: routine cleansing products are allowed).

After the completion of any study visit where a study medication treatment was performed subjects must **NOT wash/submerge** the Target or Non-Target Warts for at least **6 hours** and must not apply any topical products to the Target or Non-Target Warts for at least **6 hours**.

7.9. Breaking the Blind

The blind may be broken ONLY in the event of a medical emergency, in which knowledge of the study medication identity is critical to the management of the subject's course of treatment. Before breaking the blind the investigator should determine that the information is necessary. In many cases, particularly when the emergency is clearly not study medication-related, the problem may be effectively managed by assuming that the subject is receiving an active study medication without the need for unblinding.

If deemed necessary to break the blind for a study subject, attempt to contact the Medical Monitor to obtain permission to break the blind of a particular subject. If it is not possible to contact the Medical Monitor beforehand, contact her/him as soon as possible after breaking the blind for a subject.

Page 31 of 53 Amendment 2 Version 3 Date: 05 December 2017 To identify a subject's study medication, locate the second panel of the tear-off label from the Subject Kit attached to the subject's Label Page CRF and follow the instructions on the label. Record the date of un-blinding, the reason for the un-blinding and the initials of investigational center staff member who performed the un-blinding on the subject's Label Page CRF.

At the end of the study, the original Label Page CRFs will be returned to Aclaris Therapeutics with a photocopy placed in the investigator's study file. The original Label Page CRFs will be available, upon request, to the site if needed to respond to a regulatory inspection.

8. ASSESSMENTS OF CLINICAL EFFICACY

8.1. Target and Non-Target Wart Identification

At Visit 1, the investigator will identify one Target Wart and up to 3 additional Non-Target Warts on the trunk or extremities for each subject for treatment and evaluation.

For this study, the trunk and extremities are defined as:

- The front and back of the torso from the clavicle to the hips, including the buttocks and excluding the genitals and anus
- The arms from the shoulder to the fingertips, excluding periungual and subungual areas
- The legs from the hip to the ankles (including the dorsal side of the foot).

At Visit 1, each Target and Non-Target Wart must:

- Have a longest axis that is \geq 3mm and \leq 8mm
- Have a thickness ≤ 3 mm
- Be a discrete lesion
- Be, when centered in the circular cutout of the provided template, the only common wart present (Refer to Figure 2)
- Not be periungual, subungual, genital, anal, mosaic, plantar, flat or filiform.
- Not be covered with hair which, in the Investigator's opinion, would interfere with the study medication treatments or the study evaluations
- Not be in an area that may be occluded (*e.g.*, by clothing or footwear or in a skin fold).

Record the location of the Target and Non-Target Wart on the body charts in the CRFs indicating landmarks and distances to assist with confirming the location of the Target and Non-Target Warts at subsequent visits.

At Visit 1, the Investigator and an investigational staff member will identify each Target and Non-Target Wart by placing 2 identification (ID) stickers approximately 180 degrees opposite each other with the identified wart in the center of the area outlined by the provided circular template (diagram not to scale):

Figure 2 Target/Non-Target Wart Identification

At Visits 2-13, an investigational staff member (other than the evaluating investigator) will confirm the location of each Target/Non-Target Wart using an appropriate combination of the Visit 1 hard-copy reference prints, Visit 2 photographs and the body charts. The staff member will identify the Target/Non-Target Warts by placing 2 appropriately colored ID stickers, with the Target/Non-Target Wart number written on one sticker, approximately 180 degrees opposite each other with the identified wart in the center of area outlined by the provided circular template.

8.2. Standardized photography

At Visits 1, 2, 4, 9, 10, and 13 a qualified investigational center staff member will take standardized color photographs of each Target and Non-Target Wart.

The photographs are to document the appearance and location of the subjects' Target and Non-Target Warts. The subject's identity will not be revealed in the study photographs.

At Visit 2, the photographs must be taken prior to the study medication application.

Care must be taken to ensure the same lighting, background, subject positioning relative to the camera and camera settings are used for each photograph.

Page 33 of 53 Amendment 2 Version 3 Date: 05 December 2017 Sites will be provided with photography equipment and supplies necessary for obtaining the Target Lesion photographs. Detailed instructions for obtaining and managing the photographs will be documented in the study specific Photography Manual and provided to the site at the study initiation visit.

8.3. Physician's Wart Assessment (PWA)

The Physician's Wart Assessment (PWA) is the Investigator's assessment of the severity of each Target and Non-Target Wart at a particular time point. The Investigator should NOT refer to any other assessments to assist with this evaluation. This evaluation IS NOT a comparison with the PWA at any other visit.

At every study visit, the Investigator will assess the Target and Non-Target Warts and report the one integer that best describes the Target and Non-Target Wart severity using the following scale. At any visit where a study medication treatment is performed, the PWA must be completed prior to the treatment.

	Physician's Wart Assessment						
Grade	Descriptor						
0	Clear: No visible wart. No further treatment is indicated						
1	Near Clear: A visible wart that is less than 3mm in maximal diameter (or length)						
2	A visible wart \geq 3mm and <6 mm in maximal diameter (or length)						
3	A visible wart \geq 6mm in maximal diameter (or length)						

At Visit 1 for the subject to be enrolled and at Visit 2 for the subject to be randomized each Target and Non-Target Wart must have a PWA grade ≥ 2 .

At Visits 3-9, Target and Non-Target Warts must have a PWA > 0 to be retreated. If the Investigator cannot assess the PWA for a Target or Non-Target Wart (*e.g.*, the Target /Non-Target Wart cannot be visualized because of an LSR such as edema, scabbing, etc.) she/he must report the reason in the subject's CRFs. The Target/Non-Target Wart must not be retreated at that visit, and the subject should be seen at the next scheduled visit.

8.4. Subject Instructions

An investigational center staff member will dispense a Subject Instruction Sheet to each subject at Visit 1 (Refer to Appendix 15.1).

Throughout the study, the subjects should:

- Continue their routine cleansing regimen except they should avoid vigorous scrubbing of the Target/Non-Target Warts (*e.g.*, loofah, back brushes, scrubbing straps, abrasive washcloths, sponges and cleansing pads, etc.)
- Continue their routine cosmetics and skin care products

Page 34 of 53 Amendment 2 Version 3 Date: 05 December 2017

- Avoid exposing the Target/Non-Target Warts to excessive natural or artificial ultraviolet radiation (*e.g.*, sunlight, tanning beds) and use sunscreen on the Target/Non-Target Warts, if excessive exposure cannot be avoided
- Avoid activities that might irritate the Target/Non-Target Wart
- Avoid the use of self-tanning lotions and spray tans.
- Bring the subject instruction sheet with them to each visit.

On study visit days, the subjects should:

- When appropriate for the Target/Non-Target Wart location wear loose fitting clothing to the visit (Note: clothing that comes in contact with the study medication may be bleached)
- Starting with Visit 2, not apply any topical products to the Target/Non-Target Wart within **12 hours** prior to the visit (Note: routine cleansing products are allowed)
- After the completion of any study visit where a study medication treatment was performed DO NOT:
 - Wash/submerge the Target or Non-Target Warts for at least 6 hours
 - Apply any topical products to the Target or Non-Target Warts for at least 6 hours.

8.5. Other Study Supplies

Aclaris Therapeutics, Inc. will provide:

- An appropriate ruler, or other instrument, for measuring the thickness of all Target/Non-Target Warts dimensions
- Templates for use when identifying Target/Non-Target Warts
- Supplies and instructions for collecting, labeling, shipping and result reporting for the clinical laboratory tests and urine pregnancy tests from a third party
- Equipment, supplies and training for taking standardized photographs
- Scales to weigh all treatment applicators
- Eyewash kits.

9. ASSESSMENT OF SAFETY

In addition to reporting adverse events throughout the study the investigator, a designated and appropriately trained staff member or the subject, will perform the following safety assessments according to the schedules noted below.

The investigational staff member performing the LSR evaluations must not participate in the study medication treatment for the subject being evaluated.

9.1. Local Skin Reactions (LSR)

The LSR assessment is the Investigator's assessment of the signs and the subject's assessment of the symptoms associated with irritation at the Target/Non-Target Wart site (*i.e.*, the Target/Non-Target Wart and the skin immediately surrounding the Target/Non-Target Wart exposed to study medication). The Investigator may refer to previous photographs to assist with these assessments only after the PWA has been performed.

The Local Skin Reaction signs to be assessed are:

- Erythema
- Edema
- Erosion
- Ulceration
- Vesicles/bullae
- Excoriations
- Scabbing.

The Local Skin Reaction symptoms to be assessed (by the Subject) are:

- Stinging/burning
- Pruritus (itch).

At Visits 2-13, the Investigator will evaluate the LSR signs at the Target/Non-Target Wart site(s) as follows:

- At visits where a study medication treatment or retreatment is performed:
 - \circ Perform an LSR assessment prior to any study medication application
 - $\circ~$ For treated Target and Non-Target Warts perform an LSR assessment 20 (±4) minutes after the Treatment Completion Time.

At Visits 2-13, the Subject will assess the LSR symptoms at the Target/Non-Target Wart site(s) as follows:

- At visits where a study medication treatment or retreatment is performed:
 - Perform an LSR assessment prior to any study medication application
 - For every treated Target and Non-Target Wart site, 10 (±4) minutes after the Treatment Completion Time, report the average of the severity of the LSR for all symptoms since completion of the study medication treatment.
 - At visits where no study medication treatment is performed:
 - Perform an LSR assessment.

The Investigator and subject should report the one integer that best describes the severity of each LSR sign or LSR symptom for the Target and Non-Target Wart sites using the scale below.

Page 36 of 53 Amendment 2 Version 3 Date: 05 December 2017
Local Skin Reactions			
Grade	Descriptor		
0	None		
1	Mild		
2	Moderate		
3	Severe		

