4. STUDY DESIGN

This is a phase 2, randomized, multi-center, study designed to evaluate the safety and efficacy of A-101 45% compared to Vehicle in subjects with common warts on the trunk or extremities.

During the study, the investigator will identify 1 eligible Target Wart and up to 3 additional Non-Target Warts on each subject on the trunk or extremities. All Target and Non-Target Warts will be treated weekly for 8 weeks.

Subjects will be required to complete a total of 13 study visits. The protocol defined study visits are:

- Visit 1 (Day -13 to 0) screening
- Visit 2 (Day 1) randomization; study medication treatment
- Visit 3 (Day 8) study medication treatment
- Visit 4 (Day 15) study medication treatment
- Visit 5 (Day 22) study medication treatment
- Visit 6 (Day 29) study medication treatment
- Visit 7 (Day 36) study medication treatment
- Visit 8 (Day 43) study medication treatment
- Visit 9 (Day 50) study medication treatment
- Visit 10 (Day 57) follow up evaluations, no Target or Non-Target Wart retreatment
- Visit 11 (Day 78) follow up evaluations, no Target or Non-Target Wart retreatment
- Visit 12 (Day 106) follow up evaluations, no Target or Non-Target Wart retreatment
- Visit 13 (Day 134) follow up evaluations, no Target or Non-Target Wart retreatment; end of study

Page 16 of 53 Amendment 2 Version 3 Date: 05 December 2017 Refer to Section 6 for a complete list of protocol required study assessments.

A completed evaluable subject is a subject that misses no more than 3 treatment visits, completes Visit 10 and Visit 13 (end of study visit), has had all Target Warts assessed at these visits and has not had a protocol violation documented during the study.

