6. STUDY PROCEDURES

The schedule of study activities (including assessments, tests, exams, disease assessments, and study drug administration) beginning with screening and continuing through the end of study are outlined in Table 1. A written, signed informed consent form (ICF)/assent must be obtained from each subject prior to performing any study related procedure (e.g., vital signs, clinical laboratory sampling, urine pregnancy test or photography).

Table 1:Study Procedures

Visit	V1	V2	V3	V4	V5	V6	V7	V8	V9	V10	V11	V12	V13
	Screening												
Treatment Day	-13 to 0	1	8	15	22	29	36	43	50	57	78	106	134
Treatment Window	N/A	N/A	±1 day	±4 days	± 4	± 4	±4 days	± 4	± 4	+4	±7	±7	+7
					days	days		days	days	days	days	days	days
Study Procedures													
Informed Consent/Assent	Х												
Inclusion	Х	X^1											
Criteria/Exclusion Criteria													
Subject Identifier	X ²												
Medical	Х												
history/demographics													
Fitzpatrick Skin Type	X ³												
Assessment													
Vital Signs	X ⁴								Х				Х
Prior	X ⁵												
Medications/Therapies													
Clinical Chemistry and	Х								Х				Х
CBC ⁶													
Urine Pregnancy Test ⁷	Х	Х							Х				Х
Target Wart Identification ⁸	Х												
Physician's Wart	Х	Х	Х	Х	Х	Х	Х	Х	Х	Х	Х	Х	Х
Assessment ⁹													
Target Wart Dimensions ¹⁰	Х	Х	Х	Х	Х	Х	Х	Х	Х	Х	Х	Х	Х
Standardized	Х	Х		Х					Х	Х			Х
Photography ¹¹													
Subject Randomization		X ¹²											
Local Skin Reactions		X ¹³	Х	Х	Х	Х	Х						
Study Medication		Х	Х	Х	Х	Х	Х	Х	Х				
Application ¹⁴													
Weighing of Study		Х	Х	Х	Х	Х	Х	Х	Х				
Medication Applicators ¹⁵													
Subject Instructions	Х	Х	Х	Х	Х	Х	Х	Х	Х	Х	Х	Х	
-	1												

Page 21 of 53 Amendment 2 Version 3 Date: 05 December 2017

Concomitant therapies ¹⁶	Х	Х	Х	Х	Х	Х	Х	Х	Х	Х	Х	Х
Adverse Events ¹⁷	Х	Х	Х	Х	Х	Х	Х	Х	Х	Х		

¹Subject inclusion/exclusion criteria will be re-assessed prior to randomization during Visit 2.

²Investigational sites will assign a unique five-digit subject identifier to each subject at Visit 1. This subject identifier will be used in all study documentation for the duration of the study.

³Each subject's skin must be assessed during Visit 1 using the Fitzpatrick Skin Type Assessment. Refer to Section 9.5.1 for the scale.

⁴Vital signs [including temperature, pulse, respiratory rate, blood pressure, height and weight (Visit 1 only)] will be measured by a qualified staff member at Visit 1, Visit 9 and Visit 13.

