¹³ The investigator and subject will assess each Target Wart for local skin reactions associated with irritation at Visits 2-13. At Visit 2-Visit 9, the investigator and subject will assess the Target and Non-Target Warts for LSRs prior to the application of the study medication. The subject will assess LSRs 10 (\pm 4) minutes after the application of A-101 study medication and the investigator will assess for LSRs 20 (\pm 4) minutes after application of A-101 study medication. Refer to Section 9.1 for the complete list of Local Skin Reaction signs and symptoms.

¹⁴The investigator will apply the A-101 study medication to subject 8 to 17 years of age. Subjects 18 years of age and older will apply their A-101 study medication in the presence of the treating physician or a member of the investigational study staff that has been trained on the protocol. All Target and Non-Target Warts will be treated with study medication following randomization at Visit 2. If a Target or Non-Target Wart meets the criteria for re-treatment as defined in Section 7.6 the lesion will be re-treated at Visit 3-9. Following application of study medication, subjects must NOT wash/submerge the Target or Non-Target Warts for at least 6 hours and they must NOT apply any topical products to the Target or Non-Target Warts for at least 6 hours.

Page 22 of 53 Amendment 2 Version 3 Date: 05 December 2017 ¹⁵Sites will be required to weigh all A-101 study medication applicators before and after treatment and document the weight of each applicator in the subject's eCRF.

¹⁶All concomitant therapies including (topical and oral) prescription medications, over the counter medications and natural supplements and non-drug therapies including chiropractic, physical therapy, and energy based therapy must be documented in the subject CRF. Subjects must not apply any topical products (e.g., moisturizers, sunscreen, etc.) to their Target or Non-Target Warts within 12 hours prior to any study visit.

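### The Table 1 marks for local skin reactions (V2-V7) contradict footnote 13 and Section 9.1 (Visits 2-13), and the investigator's list in 9.1 gives no procedure for visits without treatment

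*Protocol*

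**What the plan says.** The LSR schedule is stated in three places in the protocol, and each is repeated in the SAP.

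- **Table 1 grid** (protocol Section 6; SAP Section 4). The row "Local Skin Reactions" has marks at V2 to V7 and empty cells at V8 to V13.
- **Footnote 13**, attached to that row at V2. "The investigator and subject will assess each Target Wart for local skin reactions associated with irritation at Visits 2-13". It continues: "At Visit 2-Visit 9, the investigator and subject will assess the Target and Non-Target Warts for LSRs prior to the application". It then adds checks after application, by the subject at 10 minutes and the investigator at 20 minutes.
- **Section 9.1** (SAP 6.1). The investigator's part opens: "At Visits 2-13, the Investigator will evaluate the LSR signs at the Target/Non-Target Wart site(s) as follows". The only case listed beneath it is "At visits where a study medication treatment or retreatment is performed". The subject's part covers the same visits and lists that case and a second one, "At visits where no study medication treatment is performed", with an instruction to assess LSRs then too.

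The two treatment visits that the grid leaves blank are listed in Section 4 as "Visit 8 (Day 43) study medication treatment" and "Visit 9 (Day 50) study medication treatment". Section 7.6 withholds retreatment of a wart at Visits 3-9 when its pre-treatment LSR grade is severe and has risen since the previous visit.

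**The concern.** Visit worksheets and eCRF pages are commonly built from the schedule grid. If that happened here, no LSR would be recorded from V8 onward, although the text asks for it.

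Three things depend on those records. The Section 7.6 rule needs a pre-treatment grade at V8 and V9, and it compares each visit with the one before, so a missing V8 grade also removes the comparator at V9. The SAP (Section 8.5 and Tables 14.3.5.1 to 14.3.5.6) summarises LSR by visit, with separate subject-rated and investigator-rated tables, so collection that differed by site would leave unequal denominators from V8. Finally, Section 2.2 describes the reactions in the preceding study as generally transient, and graded signs at follow-up are the most direct evidence on that point here.

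Correcting the grid alone would leave a second gap. The subject rates two symptoms, while the seven signs, including erosion, ulceration, vesicles and scabbing, are the investigator's. For a visit without treatment the investigator has no listed procedure. That covers V10-V13, and also any visit from V3 to V9 at which treatment is withheld. One reason for withholding is a severe reaction that has worsened.

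**Working it through.** There is no stated figure to reproduce. The check is a visit count and a comparison of texts.

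**1. Grid against text**

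| Source | LSR visits | Count |
|---|---|---|
| Table 1 marks, protocol | V2-V7 | 6 |
| Table 1 marks, SAP | V2-V7 | 6 |
| Footnote 13, first sentence | V2-V13 | 12 |
| Section 9.1 and SAP 6.1, investigator and subject lead-ins | V2-V13 | 12 |

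Required by text but unmarked: 12 − 6 = 6 visits (V8-V13), or 6/12 = 50% of the visits after screening. These are 2 of the 8 treatment visits (V8, V9) and all 4 follow-up visits (V10-V13).

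A slipped column is an unlikely explanation. The study-medication row of the same table falls on V2-V9 in both documents, as the design requires, and the LSR row shows the same blanks in both.

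**2. What each text supplies at the unmarked visits**

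| | V8-V9 (treatment) | V10-V13 (no treatment) |
|---|---|---|
| Table 1 mark | none | none |
| Footnote 13 | first sentence, plus checks before and after application | first sentence only, naming the Target Wart |
| 9.1 investigator lead-in | yes, Target and Non-Target | yes, Target and Non-Target |
| 9.1 investigator procedure | yes, if treatment is given | none listed |
| 9.1 subject procedure | yes | yes |
| Section 7.6 needs the grade | yes | not applicable |

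**3. Reading the table**

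At V8 and V9, footnote 13, Section 9.1 and Section 7.6 all call for grading, and only the marks disagree. At V10-V13 the requirement on the investigator exists, but within Section 9.1 it rests on the lead-in, whose introductory words promise a procedure that is then given only for treatment visits. The same applies to a visit from V3 to V9 at which treatment is withheld. For Non-Target Warts at V10-V13, footnote 13 gives no support and the 9.1 lead-in is the only statement that assigns the investigator's grading to those visits.

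**The case against.** The strongest case against is that the requirement is already in the documents and only the layout is at fault. Footnote 13 is part of Table 1, and the two lead-ins of Section 9.1 agree with it. Much of this stands, and it rules out several stronger readings.

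- *Monitoring stops at V7.* A reader might infer this from the blank cells. The documents do not support it: the footnote on that row runs to Visit 13, and at V8 and V9 the retreatment rule cannot be applied without a grade.
- *Signs are unspecified at follow-up.* A reader might infer this from the missing line. The 9.1 lead-in assigns signs to the investigator at V10-V13 on Target and Non-Target Warts. The scoring sentence that closes the section names both investigator and subject. What is missing is the procedure.
- *Most treated warts are dropped from follow-up.* The first sentence of footnote 13 names only the Target Wart, but 9.1 names both kinds.
- *Recovery after the last application cannot be shown.* It can be shown in part. Subjects score symptoms at V10-V13. LSR-related clinical adverse events are exempt from the V11 cut-off in footnote 17. Related adverse events are followed until resolved or stable (Section 10.2.1). Photographs are taken at V10 and V13.

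It is also fair that loss of data depends on the eCRF, which is not in the documents, and that safety is summarised without inferential testing (Section 12.3; SAP 9.2).

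The contradiction itself remains. Nothing says which statement governs if grid and text differ, the same blanks stand in both documents, and two of the blank visits feed a retreatment decision.

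**Conclusion.** The point holds as an internal inconsistency in a descriptive safety measure. It is not a design choice and does not touch the primary endpoint. Two defects are established: the marks cover 6 visits where footnote 13 and Section 9.1 require 12, and the investigator's list lacks the untreated-visit line that the subject's list has. Both appear in the protocol and the SAP.

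The possible loss ranges from none, if sites and eCRF follow the text, to LSR data at 6 of 12 visits, if they follow the grid. At the upper end the by-visit LSR tables would be incomplete from V8. The upper figure rests on the assumption that the grid is used to build worksheets or eCRF pages, which the documents neither confirm nor exclude. It is worth correcting despite that uncertainty, because the grade is an input to Section 7.6 at V8 and V9 and the correction is small.

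**What to change.** Reconcile the passages in both documents.

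1. Mark the LSR row of Table 1 at V8-V13 in the protocol and SAP, to agree with footnote 13 and Section 9.1.
2. In the investigator's list of Section 9.1 and SAP 6.1, add the line that the subject's list already has: at a visit without treatment, carry out an LSR assessment.
3. In the first sentence of footnote 13, name Non-Target Warts beside the Target Wart, as 9.1 does.
4. Check that the eCRF collects LSR at V8-V13, for signs and symptoms.

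The cost is a table and wording correction in two documents and an eCRF check. No visit or staff is added, since the investigator already examines every Target and Non-Target Wart for the PWA at each of these visits.
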